9.4 Pharmacokinetic Analysis

The pharmacokinetic analysis will be described in a separate pharmacokinetic analysis plan.

9.5 Other Parameters

In general, other analyses by visit will only include all cycles until Cycle 6, Cycle 12 and EOS.

9.5.1 Cytokines

Cytokines will be measured at Day 1, Cycle 1 before study drug administration and 2 hours after end of study drug administration. Actual values and absolute and percent changes from pre-administration to post-administration will be summarised descriptively. Moreover, 95% confidence intervals will be provided for mean and median changes in summaries of

absolute changes from baseline and for median changes in summaries of percentage changes from baseline in combined presentations.

9.5.2 Bone / Skeletal Survey

Bone/skeletal survey by x-ray, computer tomography or magnetic resonance imaging will only be performed at screening and EOS where medically indicated as a regular assessment of standard care. Thus, the data of bone/skeletal surveys will only be listed.

9.5.3 Quality of Life

Standardized scores for quality of life for all categories (scales) will be calculated as described in section 7.3.5. The standardized scores and the absolute changes from baseline will be summarized descriptively by visit. Moreover, 95%-confidence intervals will be provided for mean and median changes in summaries of absolute change from baseline for combined data.

10. SAFETY AND TOLERABILITY ANALYSES

The analysis of safety assessments in this study will include summaries of the following categories of safety data collected for each subject:

- Adverse Events (AEs), i.e. pre-treatment AEs, treatment emergent AEs (TEAEs), and Serious AEs (SAEs)
- AEs leading to discontinuation
- Any deaths
- Dose-limiting toxicities
- Infusion reactions
- Clinical laboratory investigations (hematology, serum chemistry, coagulation, endocrinology, urinalysis)
- Vital signs (blood pressure, heart rate, respiratory rate, body temperature)
- Electrocardiogram (ECG) results
- Physical examination results
- Exposure to study drug
- Discontinued subjects

10.1 Dose Limiting Toxicities and Maximum Tolerated Dose

One of the primary endpoints will be to determine the MTD or recommended dose and dosing regimen for MOR03087 with or without DEX and in combination with 2 standard IMiD therapies, Lenalidomide and Pomalidomide. This primary endpoint will be determined in the DLT Evaluable Population and will be based on a 4-week safety assessment period (one 28-day cycle).

Following completion of Parts A-C (dose escalation of MOR03087 alone and in combination with DEX using 2 dosing schedules), the MTD and/or recommended dose will be confirmed in a minimum of 6 subjects. Following completion of Parts D and E (dose escalation of MOR03087

in combination with POM + DEX and in combination with LEN + DEX), the MTD and/or recommended dose in each treatment arm will be confirmed in a minimum of 6 subjects.

The recommended doses for the confirmation cohorts will be determined after review of all available safety data from the corresponding dose escalation portion of the study and based on the recommendation of the DMC. The recommended dose may be the MTD or a dose below the MTD.

The MTD is defined as the dose level below the dose level at which 2 out of 3 subjects or 2 out of 6 subjects experience a DLT, as described in the dose-escalation plan (see section 3.1).

All DLTs will be entered as AEs on the Adverse Event Page and identified by the investigator as DLTs by ticking the corresponding field (dose limiting toxicity yes/no). Moreover, there is an additional field on the AE page (hidden for site entry) which contains the information regarding whether the AE is a DLT according to the decision of the sponsor assessment or DMC as documented in the meeting minutes. The additional DLT field will not need to be filled out in case of unambiguous cases.

Thus, the analysis of DLTs will be described within the subsequent sections covering the analysis of AEs. For DLT analyses, DLTs will be filtered based on the following approach. If the field "DLT as per sponsor assessment or DMC decision" is filled out, this field will be used to determine if AE is a DLT, otherwise the field "Is this Adverse Event a Dose-Limiting Toxicity?", which is filled out by the Investigator, will be used.

The DLT summaries will only be presented for the first cycle, as the DLT period covers Day 1 of Cycle 1 (starting with first study drug administration) until Day 29 (before start of the second cycle). DLTs occurring in subjects from the confirmation cohorts will be included.

10.2 Adverse Events

All TEAEs and SAEs will be coded using MedDRA (MedDRA Version 20.1, and updated to the newest version 23.0 for the follow-up analyses).

The body systems 'Blood and lymphatic system disorders' and 'Investigations' will be combined for the purpose of analysis. Moreover, all preferred terms from those two body systems that are subsequently listed in the same row will be combined:

- Red blood cell count decreased / Haemoglobin decreased / Haematocrit decreased / Mean cell volume decreased / Anaemia
- Fibrin D dimer increased / International normalised ratio increased / Prothrombin time shortened / Coagulopathy
- Eosinophil count increased / Eosinophilia
- Blood fibrinogen increased / Hyperfibrinogenaemia
- White blood cell count increased / Leukocytosis
- White blood cell count decreased / Leukopenia
- Lymphocyte count decreased / Natural killer cell count decreased / CD4 lymphocytes decreased / B-lymphocyte count decreased / Lymphopenia
- Monocyte count decreased / Monocytopenia
- Neutrophil count decreased / Neutropenia
- Neutrophil count increased / Neutrophilia
- Plasma cells increased / Plasmacytosis
- Platelet count decreased / Thrombocytopenia

TEAEs are defined as AEs occurring or worsening after the start (date and time) of the first study treatment (any IMP) and up to 28 days after the last study treatment including all treatment cycles (treatment emergent period). However, AEs occurring or worsening later than 28 days after the last treatment with study drug are defined as treatment emergent if these are considered to be related to the study drug.

If the start date and time of an AE are partially or completely missing, the AE will be assumed to be treatment-emergent if it cannot be definitely shown that the AE did not occur or worsen during the treatment-emergent period (worst case approach). Missing dates and times will not be replaced.

Thus, the following approach will be taken:

- If the start time of an AE is missing but the start date is complete, an AE will only be excluded from TEAEs if the start day is before the day of first treatment or the start day is after the end day of the treatment-emergent period.
- If the start time and day are missing but the start month is complete, an AE will only be excluded from TEAEs if the start month is before the month of first treatment or the start

month is after the end month of the treatment-emergent period or if stop date/time is before start of first treatment.

- If the start day and months are missing but the start year is complete, an AE will only be excluded from TEAEs if the start year is before the year of first treatment or if the start year is after the end year of the treatment-emergent period or if the stop date/time is before the start of first treatment.
- If the start date is completely missing, an AE will not be excluded from TEAEs unless the stop date/time is before the start of first treatment.

Time from first treatment to onset of AE [days] will be calculated for complete dates only and will be included in listings.

The TEAE grading will be determined by the investigators according to the NCI-CTC toxicity criteria. If a subject experiences a specific type of adverse event more than once, only the maximum grading will be considered in tables of TEAEs by grading when calculating the incidences (number and percentage of subjects with AE of specific type and grade).

One of the primary endpoints will be to determine the incidence and severity of AEs.

A TEAE summary table will be presented showing the incidence and frequency of all

- Treatment-emergent AEs (TEAEs)
- TEAEs by grading (according to NCI-CTCAE toxicity criteria)
- TEAEs with Grade ≥ 3
- TEAEs with Grade 1 and 2
- TEAEs with Grade 3 and 4
- TEAEs related to MOR03087 / Pomalidomide / Lenalidomide / Dexamethasone
- Serious adverse events (SAEs)
- Serious adverse events (SAEs) related to MOR03087 / Pomalidomide / Lenalidomide / Dexamethasone
- MOR03087-related TEAEs by grading (according to NCI-CTCAE toxicity criteria)
- Pomalidomide-related TEAEs by grading (according to NCI-CTCAE toxicity criteria)
- Lenalidomide-related TEAEs by grading (according to NCI-CTCAE toxicity criteria)
- Dexamethasone-related TEAEs by grading (according to NCI-CTCAE toxicity criteria)
- DLTs
- Infusion reactions
- TEAEs leading to any action on MOR03087 / Pomalidomide / Lenalidomide / Dexamethasone
- TEAEs leading to withdrawal of MOR03087 / Pomalidomide / Lenalidomide / Dexamethasone

- TEAEs that caused the subject to withdraw from the study
- Symptomatic overdoses reported as TEAE

The incidence refers to the number and percentage of subjects with at least 1 TEAE of the specified type and the frequency to the number and percentage of AEs.

Exact 95%-confidence intervals for the incidence rates will be included in the summary tables for the combined data.

The analyses by grading will be based on the NCI-CTCAE grade (version 4.0). If the NCI-CTCAE grade is not available, this will be analyzed as “Missing”.

A further summary table of the same structure will be presented which includes only AEs with a start date in the first cycle (relevant for the determination of the MTD and recommended dose). In case of incomplete start dates, an AE will be allocated to the first cycle, if it cannot be excluded that the AE started within the first cycle based on the month or year of the incomplete start date.

Summaries of incidence rates (number and percentage of subjects) and frequencies (number and percentage of AEs) of individual TEAEs by MedDRA SOC and Preferred Term will be prepared. Such summaries will be displayed for all AEs in the following categories:

- TEAEs
- TEAEs related to MOR03087
- TEAEs related to DEX
- TEAEs related to LEN
- TEAEs related to POM
- TEAEs by maximum grading according NCI-CTCAE
- DLTs
- Infusion reactions
- TEAEs leading to withdrawal of any study drug
- TEAEs that caused the subject to withdraw from the study
- TEAEs of Grade ≥ 3
- TEAEs with Grade 1 and 2
- TEAEs with Grade 3 and 4
- SAEs
- SAEs related to any treatment
- SAEs leading to death
- SAEs leading to death related to any treatment
- Non-serious TEAEs

In these summaries each subject will be counted only once within each preferred term to calculate the incidences.

The summaries of all TEAEs (summary table + TEAEs by grading) will be repeated including only TEAEs from the first cycle. The DLT summary will only be presented for the first cycle.

The time to the first TEAE will be summarized by summary statistics (n (number of subjects with event), mean, standard deviation, median, Q1, Q3, min, max) for the following TEAEs:

- Each AESI (infusion reactions \geq grade 3, cytokine release \geq grade 3, allergic reaction to MOR03087 \geq grade 3, second primary malignancies (all grades) and DLTs (all grades)
- All PTs \geq grade 3 in SOC Infections, and per PT in SOC infections with \geq grade 3
- Hematological AEs per PT \geq grade 3 (i.e. all PTs \geq grade 3 in SOC Blood and lymphatic system disorder including the ones combined with SOC Investigations as described above, and per PT in SOC Blood and lymphatic system disorder including the ones combined with SOC Investigations as described above with \geq grade 3)
- Diarrhoea \geq grade 3

Only patients experiencing a TEAE as mentioned above will be included in the summary table. The same table will be repeated for TEAEs related to MOR03087.

Exposure-adjusted incidence rate (EAIR) will be expressed as the number of patients experiencing an AE per patient-year (PY) of exposure to treatment and is derived as the number of patients with the event divided by the sum of all patient time at risk. Time at risk is the number of years from first treatment date to first event for patients experiencing a given event, or time on treatment in years (up to 28 days after the last study treatment) for patients who did not experience the event.

EAIR will be summarized by SOC and PT for the following:

- All TEAEs
- TEAEs related to MOR03087
- TEAEs related to any study drug
- TEAEs by grading according to NCI-CTCAE
- TEAEs leading to withdrawal of any study drug
- TEAEs that caused the subject to withdraw from the study
- SAEs

In the AE listings, AEs that started prior to the administration of any study drug will be flagged as pre-treatment AEs. Any AEs that start 28 days after the last study treatment, including all treatment cycles, will be flagged as post-treatment AEs.

A special AE summary listing displaying details of the event(s) captured on the eCRF in a compact format will be provided for

- DLTs
- Infusion reactions
- AEs leading to discontinuation on MOR03087
- AEs leading to discontinuation on Pomalidomide / Lenalidomide
- SAEs

Serious adverse event reconciliation will be performed by Data Management, Clinical Research, and Premier Research Drug Safety and Pharmacovigilance via data listings, as detailed in the SAE reconciliation plan.

The sponsor will describe other AEs of special interest (i.e. infusion reactions, cytokine release, allergic reaction to MOR03087, second primary malignancies and DLTs), in addition to those reported as SAEs.

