# **12 SAFETY MONITORING**

## 12.1 Adverse Event and Serious Adverse Event Recording and Reporting

All AEs/SAEs (except non-serious AEs for screening failures) that occur after the signing of informed consent and up to the End of Study visit (or up to 28 days after the last administration of study medication, whichever is earlier), will be recorded in the eCRF and in the subject's medical records, whether or not considered by the investigator to be related to the study drug. The SAEs should thereafter be recorded in the SAE Report Form and reported to the sponsor. All AEs/SAEs should be recorded using acceptable diagnoses, if possible. For screening failure subjects the non-serious AEs will not be recorded in the eCRF but only in the subject's medical records. The SAEs for screening failures will only be recorded until (including) the day when a subject is officially declared as screening failure.

Infusion reactions of grade 3 and higher, cytokine release syndrome, or allergic reaction to MOR03087, which are AEs of special interest in this study, should be reported along with their respective symptoms (e.g., urticaria, chills, and pyrexia for infusion reaction). If an AE has already been reported, it is not necessary to report each individual sign and symptom of that AE as a separate AE. For example, if myocardial infarction is reported as an AE, there is no need to report elevated creatine phosphokinase and abnormal ECG, or other related signs, symptoms, or laboratory values as separate AEs. However, if both occurred in isolation and myocardial infarction was not diagnosed, then each event would be reported as an AE.

Second primary malignancies will be monitored as events of special interest regardless of the treatment arm the subject is in. This includes any second primary malignancy, regardless of causal relationship to IP occurring at any time for the duration of the study. Events of second primary malignancy are to be reported using the SAE report form and must be considered an "Important Medical Event" if no other serious criteria apply. Documentation on the diagnosis of the second primary malignancy must be provided at the time of reporting (e.g., any confirmatory histology or cytology results, x-rays, CT scans, etc.).

The intensity of all AEs will be graded as mild, moderate, or severe using the following definitions:

- Mild: Tolerable
- Moderate: Interferes with normal activity

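### The SAP's only summary specific to second primary malignancies is limited to treatment-emergent events, so a case starting more than 28 days after last treatment and considered unrelated is left out of it

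*SAP*

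**What the plan says.** **Capture.** Protocol 12.1 makes second primary malignancies events of special interest whatever the treatment arm: "This includes any second primary malignancy, regardless of causal relationship to IP occurring at any time for the duration of the study". It adds: "Events of second primary malignancy are to be reported using the SAE report form". A case that meets no other seriousness criterion must be classed as an important medical event, so every case is an SAE. Protocol 10.1.12 assesses adverse events at each follow-up visit, and Protocol 7.1 caps follow-up at 3 years from first dose.

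**Recording.** The general recording rule in the same Protocol 12.1 closes at the final study visit or sooner: "or up to 28 days after the last administration of study medication, whichever is earlier), will be recorded in the eCRF". It states no exception for second primary malignancies.

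**Analysis.** SAP 10.2 counts an event as treatment-emergent if it occurs or worsens after first treatment and "up to 28 days after the last study treatment including all treatment cycles (treatment emergent period". Later events "are defined as treatment emergent if these are considered to be related to the study drug". The table of time to first TEAE has a row for "second primary malignancies (all grades", and "Only patients experiencing a TEAE as mentioned above will be included in the summary table".

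**The concern.** The protocol sets aside both timing and causality for this one event. The summary row brings both back: once 28 days have passed since last treatment, the relationship assessment alone decides whether a case is shown. Second primary malignancy is a late harm and was singled out as an event of special interest in a trial that includes lenalidomide and pomalidomide combinations. A count that closes 28 days after treatment can only be too low against the protocol's own scope. The shortfall falls on subjects who stop treatment early and are followed longest.

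Longer follow-up does not repair this. SAP 4.3 plans a long-term safety analysis by re-running everything in the SAP. Re-running a row with this restriction adds no late case considered unrelated, however long subjects are followed.

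**Working it through.** The plan gives no figure on this point. The check is a comparison of definitions, followed by day arithmetic.

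**Step 1: which cases the row keeps.**

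| Start of malignancy | Relationship | In protocol scope (12.1) | TEAE (SAP 10.2) | In the row |
|---|---|---|---|---|
| Up to 28 days after last treatment | Any | Yes | Yes | Yes |
| Later than 28 days | Related | Yes | Yes | Yes |
| Later than 28 days | Unrelated | Yes | No | **No** |

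**Step 2: whether another output in SAP 10.2 fills the gap.**

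- *Overview table.* It has an SAE line, but incidence is defined there as subjects with at least one TEAE of the given type. Read literally, this restricts the SAE line too.
- *Tables by system organ class and preferred term.* The introductory sentence refers to TEAEs, yet the SAE entry under it carries no such label. SAP 10 lists SAEs separately from TEAEs. The text supports either reading. Even if late SAEs are included, different malignancies fall under different preferred terms and are not grouped.
- *Exposure-adjusted rate for SAEs.* Subjects with the event contribute time to first event. Subjects without it contribute time only to 28 days after last treatment. If late SAEs count, the numerator runs past the time at risk. If they do not, late cases are missing.
- *Description of events of special interest.* It names second primary malignancies without a TEAE limit, but gives no window, population or table.
- *Listings.* Late events remain, flagged as post-treatment. A listing gives no rate.

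The row itself reports the number of subjects with an event and statistics on time to onset. It specifies no denominator, percentage or confidence interval.

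**Step 3: share of a 3-year period outside the window.** Inputs are 28-day cycles, last weekly treatment on Day 22 of the final cycle, a 28-day tail, and a maximum of 3 × 365 = 1,095 days.

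Last treatment day = 28 × (cycles − 1) + 22. Window end = last treatment day + 28. Share outside = (1,095 − window end) / 1,095.

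| Cycles | Last treatment | Window end | Days outside | Share |
|---|---|---|---|---|
| 2 | Day 50 | Day 78 | 1,017 | 93% |
| 6 | Day 162 | Day 190 | 905 | 83% |
| 12 | Day 330 | Day 358 | 737 | 67% |

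Counting whole cycles over 1,096 days instead gives (6 × 28 + 28) / 1,096 = 18% inside, so 82% outside. For 12 cycles, (12 × 28 + 28) / 1,096 = 33% inside, so 67% outside. The two conventions agree to within a percentage point.

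**Step 4: size of the mismatch in the exposure-adjusted rate.** On the reading that late SAEs count, a subject without the event who stops after 6 cycles and stays to 3 years contributes 190 days, against up to 1,095 days observed. The ratio is 1,095 / 190 = 5.8. After 12 cycles it is 1,095 / 358 = 3.1. On that reading the rate is too high.

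**The case against.** A reader might infer that second primary malignancies are summarised only as TEAEs, or that all late cases disappear from the report. The documents do not support this. Every case is an SAE, so it falls under the SAE overview line, the SAE tables, the SAE exposure-adjusted rate and the SAE listing. The sponsor also undertakes to describe these events separately, and late cases considered related stay in the row. The planned table list at the end of the SAP is redacted, so nobody can say that no other dedicated table exists.

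A reader might also infer that the exposure-adjusted rate is biased low. It could equally be biased high, as Step 4 shows.

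Nor does the SAP depart from the protocol's analysis section. Protocol 15.7.2 already specifies TEAE summaries together with the same undertaking on events of special interest. Protocol 12.1 governs capture and reporting.

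Finally, this is a descriptive row in an open-label phase I/IIa trial, with at least 9 subjects in each recommended-dose group, and cases will also be listed one by one.

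All of this stands, and it limits the point to the one row and to unclear SAE outputs. It does not remove the point. No readable output gives the number of subjects with any second primary malignancy over the window that the protocol set.

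**Conclusion.** The mismatch is real but narrow. The only summary specific to second primary malignancies in the readable SAP omits cases that start more than 28 days after last treatment and are considered unrelated. Those cases may appear elsewhere, but ungrouped, and in tables whose scope is ambiguous.

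The shares of about 82% and 67% are upper bounds. They apply only to a subject who stops for a reason other than progression and then stays alive, progression-free and without new anti-myeloma therapy to 3 years, because Protocol 7.1 ends follow-up visits at any of those events. Subjects whose follow-up ends soon after last treatment are unaffected. The number of cases involved is unknown and probably small.

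It should not be assumed that the data already exist. If the general recording rule in Protocol 12.1 is applied to these events, a late case may reach the safety database through the SAE form without entering the eCRF. A change to the SAP alone would then add nothing.

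**What to change.** 1. In SAP 10.2, exempt second primary malignancies from the TEAE restriction. Report the number and percentage of subjects with any case from first dose to end of study, regardless of relationship, with an exact 95% confidence interval in the combined presentations. Keep the TEAE count as a sub-row.
2. If a rate is given, use time to first malignancy for subjects with a case and time on study (already derived in SAP Table 1) for those without.
3. State whether the SAE tables and the SAE exposure-adjusted rate include events starting more than 28 days after last treatment. If the rate does, align its time at risk.
4. Reconcile the two windows in Protocol 12.1, so that late second primary malignancies reach the analysis database.

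The cost is a short SAP amendment, one small table and a clarification of the recording rule. The reported count may be slightly higher. Sample size and power do not change.
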